Participating GP surgeries will only be informed of their patient's participation in the study following receipt of informed consent. All data storage and handling will follow the principles of good clinical practice. All human tissue samples will be labelled anonymously and stored in accordance with the Human Tissue Act (2004).

4. Objectives and Outcome Measures

Primary Objectives:

The primary aim of the research is to assess the feasibility of conducting a randomised control trial to evaluate the effectiveness of a focused 15-minute one-to-one consultation in a primary care setting with a health-care professional to improve blood glucose control in pre-diabetes.

The study aims to quantify the following:

- the number of patients with an HbA1c between 42 and 47 mmolmol⁻¹ during the recruitment phase
- the percentage of patients eligible to participate who gave consent to be part of the study
- the percentage of patients who completed baseline testing; 3 month; and 6 month testing

Secondary Objectives

Secondary research questions aim to determine the impact of the consultation on the following measures at 3 and 6 months:

HbA1c

Cholesterol

BMI

Waist and hip girth

Blood pressure

Body composition

Physical activity level

Dietary habits

5. Study Design

This feasibility study will use a randomised control design to assess the effectiveness of a 15 minute one to one consultation compared to no treatment.

6. Study Setting:

All research activity included in the baseline, 3 month and 6 month visits will be completed within the [name], Aberystwyth University. The 15 minute pre-diabetes consultations will take place within Church Surgery, Aberystwyth.

7. Participant Eligibility

Participants will be eligible for participation if they are registered with Church Surgery and have an HbA1c (recorded within the last year) of between 42 and 47 mmol⁻¹.

8. Inclusion and Exclusion Criteria

Inclusion Criteria	Exclusion Criteria
Age > 18, < 80	Under judicial control
Able to provide consent	Unable to understand and follow instructions due to cognition or language problems or provide consent
Registered with a mid-Wales GP surgery	
HbA1c between 42 mmol·mol ⁻¹ and 47 mmol·mol ⁻¹	

9. Participant Identification and Recruitment

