Further information regarding the study can be sought via telephone, email or visiting the university research facility in person. Any questions the participant may have can be asked at any point prior to giving consent using any of these methods. Patients are free to withhold consent without giving reason. In accordance with the Welsh Language Act 1993, all correspondence will be translated into Welsh. For patients confirming their involvement, verbal and written informed consent will be sought in person at the start of their first visit to the Well-being Assessment Research Unit (WARU) before being inducted into the study (> 24 hours between receipt of the

study invite letter & participant information sheet and signing informed consent). Those who decline involvement will receive usual care from their GP.

13. Study Procedures

Participants will be required to visit the WARU ([name]) on 3 separate occasions, for baseline, 3 month and 6 month testing. During the baseline visit, the procedures and protocol of the study will be explained and informed consent will be received. Participant's height (Holtain Ltd, Crymych, UK) and body mass (wearing loose fitting clothing; Seca 899, Hamburg, Germany) will be collected to calculate body mass index (BMI) and waist and hip girth recorded (Seca 201, Seca GmbH & Co, Hamburg, Germany). Next, participants will be asked to sit quietly for 10 minutes in the laboratory before blood pressure is recorded from the upper non-dominant arm (Omron M3, Omron Healthcare Ltd, Milton Keynes, UK). Participants will remain seated prior to a 6 mL blood sample being obtained from the antecubital vein and collected into a heparinised vacutainer (BD Vacutainer Systems, Plymouth, UK), with minimal stasis, using standard venepuncture methods performed by a trained member of the research team. Should patients HbA1c be outside the required values during the baseline visit, they will be informed and will take no further part in the research. WARU will inform the participant's GP if their HbA1c is indicative of diabetes. Body composition will be analysed using bioelectrical impedance (Bodystat 1500, Bodystat Ltd, Douglas, British Isles).

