Upon completion of this phase of data collection, participants will be provided with a series of validated questionnaires to complete (to be completed at every visit unless otherwise stated). These include; the International Physical Activity Questionnaire- Short Form (IPAQ-SF), Food Frequency Questionnaire (FFQ; EPIC-Norfolk; baseline and 6 months), SF-36 (36-Item Short Form Survey Instrument) and components of the Personal Diabetes Questionnaire (baseline). Participants will complete the questionnaires unassisted although members of the research team will be available to answer any questions the participant may have relating to the questionnaires. Lastly, participants will receive instructions on the use of the urine collection kit for dietary monitoring (see below) and the ActiGraph for physical activity monitoring (if randomised; see below). Participants will then be free to leave the laboratory. An additional acceptability questionnaire designed by the research team will be given to participants at the end of the 6 month visit and will include questions relating to the WARU visits, 15 minute consultation (if received), urine collection and ActiGraph use. Visits will last between approximately 120 minutes and 150 minutes depending on the time taken for participants to complete the relevant questionnaires.

Following completion of the baseline visit, participants will be randomised into either the intervention group (INT) or the control group (CON). Randomisation will be achieved using a minimisation software package (Minim) and will ensure that there will be only minor differences between groups in the variables used in the allocation process. Participants in INT will receive a focussed 15 minute one to one consultation with a practice nurse at their registered general practice. The consultation derives from the original 30 minute protocol employed during a previous study conducted by the present research team (Thatcher and Gregory, 2017) which used 104 GP-registered patients. The first half of the 30 minute consultation in that study (led by general practise) collected baseline data (height, weight, waist circumference, blood pressure)

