Administration of the International Physical Activity Questionnaire Short Form	3	10 minutes	[name] or other member of the research team. This will take place in the [name] at Aberystwyth University
Administration of the Food Frequency Questionnaire	2	15 minutes	[name] or other member of the research team. This will take place in the [name] at Aberystwyth University
36-Item Short Form Health Survey Instrument	3	10 minutes	[name] or other member of the research team. This will take place in the [name] at Aberystwyth University
Components of the Personal Diabetes Questionnaire	1	10 minutes	[name] or other member of the research team. This will take place in the [name] at Aberystwyth University
15 minutes pre-diabetes consultation (if randomised to receive)	1	15 minutes	Performed by a practice nurse at a mid-Wales General Practise
End of Study Feedback questionnaire	1	10 minutes	[name] or other member of the research team. This will take place in the [name] at Aberystwyth University

18. Withdrawal Criteria

Participants are free to withdraw from the study at any time without giving prior warning or reason for withdrawal. Participants will not be replaced if withdrawn. Recruitment will continue for the first 6 months of the study. New participants will receive unique individual participant numbers.

19. Storage and Analysis of Clinical Samples

Blood Treatment:

A 1 mL aliquot of whole blood will be transferred from the heparinised vacutainer into a 1.5 mL Eppendorf. The remaining whole blood will be centrifuged at 1500 g for 10 minutes at 4°C. The separated plasma will be pipetted evenly into two separate eppendorfs and frozen at -80°C for subsequent analysis of metabolic content using FIE-MS and GC-MS. Two 1.5 µL aliquots of whole blood will be transferred from the 1.mL aliquot into separate test cartridges and will be analysed for HbA1c and lipid profile by an automated point of care blood analyser (Afinion 2, Abbot, Cheshire, UK).

Urine Treatment:

Urine samples will be centrifuged at 1500 g for 10 minutes at 4°C. 1ml of supernatant will be pipetted evenly into two separate eppendorfs and frozen at -80°C prior to analysis of metabolic content using FIE-MS and GC-MS.

20. End of Trial

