The testing stage of this study will be defined as finished when the last participant completes the final visit (6 month testing). Additionally, the research will be stopped if there is a lack of

recruitment after 6 months or if a clinical or research incident prompts a review.

21. Statistics and Data Analysis

A computerized statistical package will be used to analyse all data associated with the primary and secondary outcomes (SPSS version 17.0, SPSS inc., Chicago, IL). Normally distributed data will be presented as mean \pm SD. Scores from the questionnaires will be calculated based upon their respective scoring protocols. A two factor mixed model ANOVA will be conducted on all physiological measures and questionnaire responses to determine any differences between groups over time. Significant differences identified by the ANOVA will be further analysed by post hoc independent or paired t-tests with Bonferroni correction. Data mining of urine samples using methods such as PCA will be employed to determine if foods can be discriminated. Statistical significance will be accepted at $P < 0.05$.

22. Sample Size Calculation

The sample size was decided based upon potential numbers of eligible patients provided to the research team by the participating general practice. Potential numbers are based upon the amount of registered patients with a $\text{BMI} > 25 \text{ kg/m}^2$ or an existing $\text{HbA1c} < 12$ months. As this is a feasibility study for a future large scale randomised control trial, no formal sample size calculation has been employed.

23. Planned Recruitment Rate

Previous work completed by the research team demonstrated an approximate 50% uptake in consultation offers in patients with pre-diabetes ($n = 420$). Our partnering surgery currently have 737 patients with a $\text{BMI} > 25 \text{ kg/m}^2$. A further 216 patients have an HbA1c (recorded within the last year) within the eligible range. Furthermore, Church surgery identifies approximately 6 new

‘at risk’ individuals each week. Therefore, we estimate it will take one month to recruit 40 patients into the study.

24. Data Management

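### Does it matter that the protocol does not say how patients removed at the baseline HbA1c re-test are counted in the completion percentage or in the 40 recruits?

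*Combined protocol and SAP*

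**What the plan says.** Section 4 names three feasibility quantities. The second, the consent percentage, has a stated base: eligible patients. The third, "the percentage of patients who completed baseline testing; 3 month; and 6 month testing", has none.

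The order of events is in Sections 12 and 13. Under Section 12, "written informed consent will be sought in person at the start of their first visit". At that visit blood is drawn, and Section 13 adds: "Should patients HbA1c be outside the required values during the baseline visit, they will be informed and will take no further part" in the research. Body composition and the questionnaires are described after that rule. Then: "Following completion of the baseline visit, participants will be randomised into either the intervention group" or the control group.

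On numbers, Section 23 says "we estimate it will take one month to recruit 40 patients into the study", and Section 22 states that no formal sample size calculation was made. Section 18 says "Participants will not be replaced if withdrawn", keeps recruitment open for the first six months and does not mention re-test removals. Section 20 says "the research will be stopped if there is a lack of" recruitment after six months, without a figure. Section 21 covers ANOVA, t-tests and PCA, and gives no rule for the feasibility percentages. Figure 1, the study flow chart, is not shown in the text available for this review and may mark the exit point.

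**The concern.** The protocol creates a group that has consented and attended, is removed by rule and is never randomised, and the readable text does not say where that group is counted. Completion is a primary measure, and the study exists to judge willingness to engage and adhere before a larger trial. If removed patients count as non-completers, the figure mixes a protocol exclusion with drop-out and understates retention. If they are left out without comment, the report hides baseline visits that produced no randomised participant. It is also unclear whether a removed patient has completed baseline testing, since part of that visit comes after the removal.

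The 40 has the same double meaning. If it counts consents and removals are not made up, fewer than 40 are randomised.

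Some removals are likely. The qualifying HbA1c may be up to a year old and the eligible band is only 42 to 47 mmol/mol.

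**Working it through.** **Is there a plan figure to reproduce?** No. The 40 has no formula, power, effect size or attrition rate behind it. A plausibility check is possible: at the 50% uptake in Section 23, 40 patients need 40/0.50 = 80 eligible patients, against 216 already in range (216 × 0.50 = 108).

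**Re-test loss.** Let *r* be the share of consented patients removed. The documents do not give it. Section 2 offers only loose proxies:
- 5–10% a year progress and a similar share revert, so 10–20% a year leave the range.
- In the earlier project 44 of the 123 followed up (130 − 7) fell below 42 at 12 months: 44/123 = 35.8%. That was uncontrolled and followed a consultation.

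**Effect on the completion percentage.** Completion among consented = completion among randomised × (1 − *r*). With 85% among randomised, which is assumed:

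| *r* (assumed) | Completion among consented | Consents needed to randomise 40 |
|---|---|---|
| 5% | 0.85 × 0.95 = 80.8% | 40/0.95 → 43 |
| 10% | 0.85 × 0.90 = 76.5% | 40/0.90 → 45 |
| 20% | 0.85 × 0.80 = 68.0% | 40/0.80 = 50 |
| 35.8% | 0.85 × 0.642 = 54.6% | 40/0.642 → 63 |

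The yearly proxies overstate *r* if qualifying values are on average about six months old (also an assumption). Halved, 10%, 20% and 35.8% become 5%, 10% and about 18%, and the lowest completion figure becomes 0.85 × 0.82 ≈ 70%. Patients who enter through the BMI route have a fresh HbA1c at screening (Sections 9 and 10), so even that scaling does not describe them.

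**Can the two readings be told apart in a report?** Take 50 consented, 10 removed, 40 randomised and 34 finishing.
- Over randomised: 34/40 = 85%.
- Over consented: 34/50 = 68%.
- If removed patients have not completed baseline: baseline completion is 40/50 = 80%, and 68/80 = 85%.
- If they are counted as having completed baseline, the number randomised is needed as well. A two-arm analysis always has it.

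For a later trial, 100 completers need 100/0.85 = 117.6 randomised, or 100/0.68 = 147.1 consented, of whom 147.1 × 0.80 = 117.6 are randomised. The figures agree; each answers a different question.

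**Does the 40 come under strain?** Reaching 40 randomised at the largest loss shown takes 63 consents, and 63/216 = 29% of the patients already in range. At 20% loss it takes 50/216 = 23%. Neither share counts the 737 patients with a raised BMI or the roughly six new at-risk patients a week.

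**Consent percentage.** Consent precedes the blood test, so this looks unaffected. It does change if removed patients are reclassified as ineligible. As an illustration, 108/216 = 50%; removing 20% of the 108 (about 22) from both counts gives 86/194 = 44%. The same flow counts would show this.

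**The case for a change.** The strongest case for a change is that feasibility is the primary aim, yet one of its three measures can be read in two ways while the analysis section deals only with secondary outcomes. The sponsor wrote a removal rule and so expects removals. Even at 5% loss and no drop-out, completion among consented cannot exceed 95%. Naming the base before data are seen would cost a sentence and would prevent a later choice of the more flattering percentage. Section 23 also rests on "Previous work completed by the research team demonstrated an approximate 50% uptake in consultation offers in patients with pre-diabetes", which is not consent to a three-visit randomised study, so the recruitment estimate is less secure than it looks.

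Much of this stands as fact: the base is unstated, removals are foreseeable, and the 50% is borrowed from a different decision. What does not follow is that the plan would produce a wrong answer. The study's own counts, listed in order, fix both percentages and make a selective choice visible. Misplanning a later trial would require someone to take a percentage of consented patients for a percentage of randomised ones. A shortfall below 40 randomised needs two further readings: that 40 means consented, and that a removal is an unreplaced withdrawal. Section 18 describes withdrawal as the participant's own decision, so the second reading is strained, and recruitment stays open for six months in any case.

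**Conclusion.** The observation is correct but leads to no change. The readable text leaves the completion base and the meaning of 40 unstated. This is missing detail, not an error: no stated rule or number is shown to mislead, the counts needed for either reading arise from running the study, and an ordinary participant-flow account (eligible, consented, out of range at re-test, randomised, seen at three and six months by arm) settles the matter.

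The size is unknown. The gap between 85% and 68% depends on two assumed inputs, 20% re-test loss and 85% completion, neither of which is in the documents. With the loss proxies scaled to six-month-old values it would be smaller. The 40 is a one-month estimate with no formal sample size, and even under the heaviest loss illustrated it needs consent from under a third of the patients already in range. The missing figure for lack of recruitment in Section 20, the meaning of n = 420 in Section 23, and the 130 in Section 2 against the 104 in Section 13 for the earlier work are separate questions and do not bear on this one.

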(B) The collection of urine in the home (for the purposes of dietary analysis) has been tested rigorously in previous studies by Aberystwyth University. Previous work has shown the urine collection and storage process to be acceptable, easily conducted and understandable by a cohort of 16 free living individuals. Participants are asked to collect 3 urine samples per week for 3 weeks following each visit to the WARU. All samples are to be collected by participants the first time they urinate in the morning and therefore should not result in additional disruption to their day. The urine collection tubes will be coded anonymously with individual participant numbers and refrigerated by the participant in sealed containers until returned to the WARU by free post or in person depending on participant preference. In total, 27 urine samples will be collected across a period of 6 months.

(C) A randomly allocated sub-group of participants will be asked to wear a physical activity monitor (ActiGraph) for one week following each visit to the WARU. The monitors can simply be worn around the waist like a belt and will not interfere with daily life when worn. Participants will be asked to wear the monitor throughout the day from the time they get out of bed until they return to bed. They do not need to wear the monitor whilst washing. Participants will be asked to record the times they do not wear the monitor during the day using a simple recording sheet provided by the research team. The ActiGraph can be returned to the WARU by free post or in person depending on participant preference.

The research team will be available to assist participants via email, telephone or in person with queries relating to the dietary monitoring protocol and/or physical activity monitoring protocol.

Autonomy:

Participants will be made aware at the outset of the study that their participation is voluntary and are free to withdraw at any time without giving prior notice or reason for withdrawal. Non participation in the study or withdrawing on-going participation from the study will not compromise any current or future care participants receive from the UK National Health Service or future involvement in studies conducted by Aberystwyth University.

Confidentiality:

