and the second half provided patients with lifestyle advice on preventing diabetes. The consultation to be used in the proposed study does not require general practise to collect baseline data and therefore the consultation time has been reduced from 30 minute to 15 minutes. The consultation will provide the participant with one to one information regarding the benefits of physical activity and healthy eating. Emphasis will be placed on the importance of achieving at least 150 minutes of moderate physical activity each week as well as adhering to healthy dietary habits, based on the NHS Eatwell Guide (Eatwell Guide, 2016). Furthermore, participants will have the opportunity to discuss prediabetes with a trained practice nurse and ask any questions they may have. Participants placed in CON will not receive the consultation and will only attend visits to the WARU. Due to logistical and financial implications, a subgroup of participants will also be randomised for additional physical activity monitoring. 5 participants from INT and 5 from CON will receive an Actigraph (see below for further information on the Actigraph).

Dietary Monitoring:

Metabolic fingerprinting and metabolic profiling of human urine is able to provide a comprehensive and quantitative snapshot of dietary exposure for 12 – 24 hrs prior to urine collection. While a single sample snapshot is not representative of an individuals' habitual dietary exposure, a series of snapshots over a prolonged time period can give a robust overview of an individual's nutritional health. Previous work by IBERS has demonstrated a community based urine collection protocol ($n = 16$) as a successful and non-disruptive method for monitoring habitual diet. Participants will be provided with a urine collection kit consisting of; of 14 cm non-sterile urine collection straws 4 mL additive free evacuated vacutainer tubes and a 125 mL collection container. Once urine has been collected, the sealed vacutainer tubes will be stored in an absorbent pouch within a sealed leak-proof bag and kept in the refrigerator. All urine storage equipment and instructions are fully compliant with the UN3373 standard for Category B

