biological substances. Participants will receive instructions to fill the collection container with a mid-stream urine sample (in order to minimise the possibility of bacterial contamination from urethral contaminants; Gilbert, 2006). Any excess urine produced which is not collected in the container should be deposited within the lavatory. The tip of the transfer straw will be submerged into the urine and a 4mL vacutainer tube inserted into the transfer straw to draw the urine into the vacutainer. Any remaining urine in the container will be deposited within the lavatory. The collection container can be rinsed with tap water after each urine sample and reused for each sample collected. Vacutainer tubes will be labelled with anonymous information including participant number, sample number, weekday/weekend sample and week number. Samples will be stored in a refrigerator at 4°C for a maximum of 10 days before the sample are returned to the lab either in person or by free post for freezing at -80°C to await analysis. Participants will record the collection details of their urine samples onto a sample collection sheet (see appendices) which notes the sample number and the date and time of collection. Participants will collect 3 samples a week for 3 weeks following each WARU visit. Participants must collect two urine samples within the week on non-consecutive days (e.g. Tuesday & Thursday) and collect a third sample on either day of the weekend (Saturday/Sunday). In total, participants will collect 27 urine samples during their participation in the study. Urine samples will be analysed using laboratory based Flow Infusion High Resolution Mass Spectrometry (FIE-HRMS) which is an established method for dietary analysis using urine samples.

Physical Activity Monitoring:

Physical activity and sedentary lifestyle will be determined using ActiGraph (ActiGraph LLC, Pensacola, FL, USA) following baseline, 3 months and 6 month WARU visits. Participants will be provided with written and verbal instructions on how to operate the device. Participants will choose one week within the three week urine collection period to wear the ActiGraph.

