Participants can choose any day within the week to begin wearing the ActiGraph but must then wear it for the following 7 days unless unfeasible to do so (e.g. swimming, bathing or showering). In this instance, participants will record at what time and the amount of time they are not wearing the ActiGraph. Should participants forget to wear the device; the same procedure will be followed. Should participants miss a whole day; they must record for an extra day directly after the 7th day. An additional sheet will be provided for participants to record any time when the device is not worn. Participants do not need to wear the ActiGraph when sleeping although they must record the time they go to sleep and at what time they wake up. Participants must fit the ActiGraph in the morning as soon as it is feasible to do so. Participants can return the ActiGraph at the end of the 7 day recording period either in person or by post.

14. Randomisation Procedure

Randomisation will be achieved using a minimisation software package (Minim) and will ensure that there will be only minor differences between groups in the variables used in the allocation process. Participant details will be recorded after the first visit and inputted into the randomisation package. Following randomisation of the first participant, remaining participants will be randomly allocated into either the intervention or control based upon age (ages 60+ in both groups / equal distribution of sex and BMI 30 kg/m² + in both groups). Randomisation will be conducted primarily by the academic supervisor. Church surgery will be informed of the patients who have been randomised to receive the intervention and referral arrangements made.

15. Baseline Data

The data to be collected at baseline and in subsequent visits are directly related to pre-diabetes or to factors which contribute to diabetes risk (e.g. dietary habits and physical activity).

- Blood test: (non-fasted) measure of glycated haemoglobin, cholesterol and metabolites indicative of dietary intake
- Anthropometry: Measures body weight and size. Being overweight is a risk factor associated with diabetes
- Blood pressure: cardiovascular health is detrimentally affected by poor lifestyle and diabetes risk
- Body composition Provides an analysis of fat mass and percentage body fat
- Urine collection: Allows for the accurate analysis of dietary behaviours
- ActiGraph: Allows for the accurate recording of physical activity

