- Physical Activity Questionnaire: Provides a measure of physical activity levels
- Food frequency questionnaire: Provides a measure of dietary habits
- Health survey: Provides a indication of current perceived health status
- Components of the Personal Diabetes Questionnaire: Provides a indication of an individual's readiness to change their lifestyle behaviours following information regarding their diabetes risk

16. Clinical Study Assessments (Frequency and Duration)

Procedure	Frequency	Duration	Researcher
Venous Blood sample for measure of HbA1c (if surgery does not have a value < 12 months)	1	10 minutes	Performed by a practice nurse or GP at a mid-Wales General Practise
Recording height and weight	3	5 minutes	[name] or other member of the research team. This will take place in the [name] at Aberystwyth University
Recording waist and hip girth	3	5 minutes	[name] or other member of the research team. This will take place in the [name] at Aberystwyth University
Recording blood pressure	3	15 minutes	[name] or other member of the research team. This will take place in the [name] at Aberystwyth University
Venous blood sample	3	10 minutes	[name] or other member of the research team. This will take place in the [name] at Aberystwyth University
Body composition analysis	3	10 minutes	[name] or other member of the research team. This will take place in the [name] at Aberystwyth University
Provision of urine sample for dietary analysis	27	5 minutes	Performed by the participant 3 x per week for 3 weeks after each WARU visit. Samples collected at home.
Actigraph (if randomised to receive)	3	7 days	Performed by the participant. Actigraph worn by the subject around the waist during waking hours. Worn for one week (within each 3 week urine sampling phase) after each

		WARU visit
--	--	------------

17. Qualitative Assessments (Frequency and Duration)

Procedure	Frequency	Duration	Researcher
Providing information prior to gaining informed consent	1	30 minutes	[name] or other member of the research team. This will take place in the [name] at Aberystwyth University

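### ActiGraph wearers who know their arm choose which week and start day are recorded, so the activity comparison can be biased by an unknown, probably small amount; the start day should be assigned in advance.

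*Combined protocol and SAP*

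**What the plan says.** Section 13 (Physical Activity Monitoring) gives the wearer the choice of week: "Participants will choose one week within the three week urine collection period to wear the ActiGraph". It then gives a choice of start day: "Participants can choose any day within the week to begin wearing the ActiGraph but must then wear it for the following 7 days". The table in Section 16 repeats the arrangement for three rounds: "Worn for one week (within each 3 week urine sampling phase) after each" WARU visit. Section 3 (Participant Burden, item C) is less specific: wearers are to "wear a physical activity monitor (ActiGraph) for one week following each visit to the WARU". No section fixes the week, asks for the same week at each round, or asks why a week was chosen.

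Section 13 also says who wears the device (5 participants from each arm) and places randomisation after the baseline visit. The INT consultation stresses the importance of "achieving at least 150 minutes of moderate physical activity each week". For controls (CON), "Participants placed in CON will not receive the consultation and will only attend visits to the WARU". No blinding or sham is described. Section 4 lists physical activity level among the secondary measures at 3 and 6 months. The other activity instrument is the IPAQ-SF, which participants complete themselves at each visit.

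**The concern.** An accelerometer avoids recall and reporting bias only if the recording period is chosen without regard to the activity in it. Here the person being measured chooses the period and knows their arm. A participant who has just been given a weekly activity target has more reason than a control to avoid a week expected to be sedentary. If that happens, part of an apparent ActiGraph effect would come from which week was recorded and not from how active people were.

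Baseline is exposed too. Wear follows the baseline visit, randomisation also follows that visit, and the date of the consultation is not tied to the wear window. A baseline week can therefore fall after allocation, and possibly after coaching. Section 21 plans a two-factor mixed ANOVA of group over time, so a distorted baseline enters the same comparison.

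**Working it through.** The plan gives no SD, effect size or power for activity, so there is no figure of its own to reproduce. The steps below bound the bias and set it against the precision available.

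**Inputs from the protocol.** One week out of three, free start day, three rounds (Sections 13 and 16); 5 wearers per arm (Section 13); significance at P < 0.05 (Section 21; I take it as two-sided).

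**Assumptions not in the protocol.** Weekly means are normal and independent within a person. The week-to-week intraclass correlation (ICC) lies between 0.5 and 0.9.

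**1. When bias arises.** Let b(g,t) be the mean shift from week selection in arm g at round t.
- Bias in the between-arm difference at round t: b(INT,t) − b(CON,t).
- Bias in the between-arm difference in change from baseline: [b(INT,t) − b(INT,0)] − [b(CON,t) − b(CON,0)].

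Both are zero if the arms choose alike. The second is also zero if each arm selects equally strongly at every round.

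**2. Ceiling.** Suppose every INT wearer picks the most active of three weeks with perfect foresight and CON wearers pick at random. The shift is the expected maximum of three standard normals, 3/(2√π) = 0.846 within-person weekly SD (simulation: 0.847).

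**3. In total-SD units.** Multiply by √(1 − ICC):

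| Assumed ICC | All INT wearers select | Half of them select |
|---|---|---|
| 0.5 | 0.846 × 0.707 = 0.60 | 0.30 |
| 0.7 | 0.846 × 0.548 = 0.46 | 0.23 |
| 0.8 | 0.846 × 0.447 = 0.38 | 0.19 |
| 0.9 | 0.846 × 0.316 = 0.27 | 0.13 |

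**4. Free start day.** If the seven days must lie inside 21, there are 21 − 7 + 1 = 15 possible windows. With independent days and perfect foresight, the simulated ceiling rises to about 1.23 weekly SD.

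**5. Precision.** For a single-round comparison with 5 per arm, SE = √(2/5) = 0.63 SD. The 95% half-width is 2.306 × 0.632 = 1.46 total SD (t on 8 df). Total SD cannot be smaller than within-person SD, so this exceeds both the 0.85 and the 1.23 ceiling whatever the ICC.

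**6. Effect on false positives.** With no true effect, a shift of 0.27 to 0.60 SD raises the two-sided rejection rate of a t-test with 5 per arm from 5% to about 7% to 13% (noncentral t, 8 df).

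**7. Carry-over.** Selection bias does not shrink with sample size, but the half-width does. By normal approximation, 1.96 × √(2/n) equals 0.60 at n = 2 × (1.96/0.60)² ≈ 21 wearers per arm, and 0.27 at n = 2 × (1.96/0.27)² ≈ 105. Beyond those sizes the ceiling bias would exceed the sampling error.

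**The case against.** The strongest reply is that this is a convenience provision in a 10-person subgroup of a feasibility study. The week is chosen in advance and not picked from three recorded weeks, so foresight is partial at best. Convenience may drive the choice, and the direction is then uncertain. Controls choose as well, and the invitation letter (Section 9) tells all invitees about steps to avoid diabetes, so the incentive is not confined to INT. The primary aims in Section 4 are counts and percentages that this cannot touch. Section 3 sets out to minimise burden, and acceptability of the ActiGraph is itself assessed at the end. All of this stands and limits severity. It does not change the fact that the rule leaves timing to people who know their arm.

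Three stronger readings are tempting and not supported:

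- **A bias in minutes.** With an assumed week-to-week SD of 40 to 60 min, 0.85 × 40 = 34 and 0.85 × 60 = 51 min/week, or 23% to 34% of the 150-minute target. The protocol gives no such SD, and the figures need perfect foresight and selection in INT only. They are a ceiling on assumed inputs, not an estimate.
- **A contradiction between Sections 3 and 13.** The looser sentence in Section 3 is compatible with one week inside the three weeks after the visit. It omits the choice and should be aligned, but it does not conflict.
- **The ActiGraph as the designated check on the IPAQ-SF.** The protocol gives it no such role. The questionnaire is completed at the visit and the monitor is worn afterwards, by a subgroup only.

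**Conclusion.** The point holds as a minor design weakness. Sections 13 and 16 let recording time depend on the outcome, and the incentive to use that freedom differs by arm. That participants know their arm is inferred from the no-consultation comparator and the absence of any described blinding.

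The bias lies between zero and about 0.85 within-person weekly SD, or 0.27 to 0.60 total SD for an assumed ICC of 0.9 to 0.5. The free start day could raise the theoretical ceiling to about 1.23 weekly SD. The upper values need perfect foresight, independent weeks (or days) and selection only in INT, and the true value may be close to zero. A reader might infer that the ActiGraph results of this study would be misleading because of week selection. The documents do not support that: imprecision with 5 per arm is larger than the ceiling, and the comparison could not be conclusive either way. The reason to act now is that this study tests procedures for a larger trial, where precision would improve and the bias would not.

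**What to change.** In Section 13, replace the participant's choice of week and start day with a start day assigned in advance by the research team, using the same rule in both arms and at baseline, 3 and 6 months. One example is seven days from the morning after the WARU visit. Allow deferral only for a reason recorded before wear begins. Keep the existing extra-day rule for a missed whole day.

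Complete the baseline wear week before allocation is disclosed. Because the subgroup takes 5 from each arm, the team may need to allocate first. In that case, hold back disclosure to the wearer, and the notice to the surgery under Section 14, until that week is finished.

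Align Sections 3, 13 and 16 and the participant instruction sheet, so that the Section 16 table does not keep the old three-week wording.

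The cost is a wording change, slightly less convenience for about 10 participants, and about a week's delay in disclosing allocation to them. No sample size changes. The fix does not remove reactivity: a wearer can still be more active because the device is on, and the report should say so.
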